12.2.5 STORAGE

Storage and Stability: Irinotecan vials must be stored in a cool, dry place, protected from light in a locked cabinet accessible only to authorized individuals. Store at 20° to 25°C (68° to 77°F); excursions permitted to 15° to 30°C (59° to 86°F). Protect from light. Do not freeze. It is recommended that the vial should remain in the carton until the time of use. It is stable for at least three years at room temperature. Irinotecan is stable for 24 hours in glass bottles or plastic bags after reconstitution with D5W.

Reconstitution and Administration: Irinotecan will be diluted with D5W to a total volume of 500 ml and infused intravenously over 90 minutes, per institutional standards. Nothing else should be added to the bag.

12.2.6 ACCOUNTABILITY

The Investigator will maintain records of each dose of chemotherapeutic drug given. The records will document dose, infusion rate, date given and time given, as per standard of care

for Irinotecan. Drug accountability records must be readily available for inspection by representatives of Amgen and by regulatory authorities. Empty and partially used vials should be accounted for and destroyed at the study site in accordance with the internal standard operating procedures.

12.2.7 IRINOTECAN DRUG ORDERING

Irinotecan is commercially available and will be charged to the subject's insurance as per standard of care.

13 REGULATORY OBLIGATIONS

13.1 INSTITUTIONAL REVIEW BOARD/INDEPENDENT ETHICS COMMITTEE

Before implementing this study, the protocol, the proposed informed consent form and other information to subjects, must be reviewed by a properly constituted Institutional Review Board/Independent Ethics Committee/Research Ethics Board (IRB/IEC/REB). A signed and dated statement that the protocol and informed consent have been approved by the IRB/IEC/REB must be provided to the CRAB CTC Operations Office before study initiation. Any amendments to the protocol, other than administrative ones, must be reviewed and approved by the study sponsor and Amgen.

13.2 INFORMED CONSENT

The investigator must explain to each subject (or legally authorized representative) the nature of the study, its purpose, the procedures involved, the expected duration, the potential risks and benefits involved and any discomfort it may entail. Each subject must be informed that participation in the study is voluntary and that he/she may withdraw from the study at any time and that withdrawal of consent will not affect his/her subsequent medical treatment or relationship with the treating physician.

This informed consent should be given by means of a standard written statement, written in non-technical language. The subject should read and consider the statement before signing and dating it, and should be given a copy of the signed document. If the subject cannot read or sign the documents, oral presentation may be made or signature given by the subject's legally appointed representative, if witnessed by a person not involved in the study, mentioning that the subject could not read or sign the documents. No subject can enter the study before his/her informed consent has been obtained.

The informed consent form is considered to be part of the protocol, and must be submitted by the investigator with it for IRB/IEC/REB approval.

13.3 COMPLIANCE WITH LAWS AND REGULATIONS

The study will be conducted in accordance with U.S. Food and Drug Administration (FDA) and International Conference on Harmonization (ICH) Guidelines for Good Clinical Practice

(GCP), the Declaration of Helsinki, Health Canada, any applicable local health authority, and Institutional Review Board (IRB) or Ethics Committee requirements.

This study must have the approval of a properly constituted IRB or Ethics Committee. Before the investigational drug is shipped to the Investigator, the Investigator or designee will provide Amgen with a copy of the IRB or Ethics Committee approval letter stating that the study protocol and any subsequent amendments and informed consent form have been reviewed and approved.

The site Investigator or designee will be responsible for obtaining continuing and not less than annual IRB or Ethics Committee reapproval throughout the duration of the study. Copies of the Investigator's annual report and other significant protocol updates to the FDA, IRB or Ethics Committee and copies of the IRB or Ethics Committee continuance of approval must be provided by the CRAB CTC Operations Office to Amgen via email PRA Health Services:

> PRA Contact: [name] Manager, Investigator Sponsored Studies PRA Health Sciences Email: [contact] [contact]

The site Investigator is also responsible for notifying the FDA, their IRB or Ethics Committee of any significant adverse events that are serious and/or unexpected.

Amgen will provide study sites and the CRAB CTC Operations Office with any expedited safety reports generated from any ongoing studies with carfilzomib, changes to the Investigator's Brochure, and any other safety information which changes the risk/benefit profile of carfilzomib during the conduct of the study, to allow him/her to fulfill his/her obligation for timely reporting to the IRB/ECs and other Investigators participating in the study.

Upon completion of the trial, the Investigator must provide the IRB or Ethics Committee and Amgen with a summary of the trial's outcome.

13.4 REGULATORY DOCUMENTATION REQUIREMENTS

c. The documents listed below must be submitted to the CRAB CTC Operations Office prior to the site's activation of CTC 11-001. Subject registration will not be permitted until all documents have been received. Documents may be submitted via Fax or email to:

CRAB CTC Operations Office – Regulatory Affairs [contact] Email: [contact]

- Investigator Signature sheet
- IRB protocol and consent form approval letter (s)
- IRB approved consent form
- OHRP Federal Wide Assurance number
- IRB membership list if available
- FDA Form 1572
- Curriculum Vitaes, Financial Disclosure forms, and Medical Licenses for all investigators and sub-investigators listed on the FDA Form 1572
- Laboratory certification and normal ranges
- d. Updates to the documents specified above must be submitted to the CRAB CTC

Operations Office during the course of the study and will include at the minimum:

- IRB protocol approval letters for annual, continuing, or modification reviews
- IRB approval of modified consent form
- Investigator Signature sheet for each version of the protocol
- Updated Form 1572 to document changes in investigators or sub-investigators

13.5 SUBJECT CONFIDENTIALITY

Subject medical information obtained as part of this study is confidential, and must not be disclosed to third parties, except as noted below. The subject may request in writing that medical information be given to his/her personal physician.

The Investigator/Institution will permit direct access to source data and documents by Amgen, its designee, the FDA and/or other applicable regulatory authority. The access may consist of trial-related monitoring, audits, IRB or Ethics Committee reviews, and FDA inspections.

Release of research results should preserve the privacy of medical information and must be carried out in accordance with Department of Health and Human Services Standards for Privacy of Individually Identifiable Health Information, 45 CFR 164.508.

14 ADMINISTRATIVE AND LEGAL OBLIGATIONS

14.1 PROTOCOL AMENDMENTS OR CHANGES IN STUDY CONDUCT

Any change or addition (excluding administrative) to this protocol requires a written protocol amendment from the CRAB CTC Operations Office. All amendments must be approved by the Sponsor-Investigator, CRAB CTC, and Amgen before implementation. Amendments significantly affecting the safety of subjects, the scope of the investigation or the scientific quality of the study require additional approval by the central IRB at each study. A copy of the written approval of the IRB must be provided to the CRAB CTC Operations Office. Examples of amendments requiring such approval are:

- 1. increases in drug dose or duration of exposure of subjects;
- 2. significant changes in the study design (e.g. addition or deletion of a control group);
- 3. increases in the number of invasive procedures; and
- 4. addition or deletion of a test procedure required for monitoring of safety.

These requirements for approval should in no way prevent any immediate action from being taken by the investigator, by the CRAB CTC, or by Amgen in the interests of preserving the safety of all subjects included in the trial. If an immediate change to the protocol is felt to be necessary by the investigator and is implemented for safety reasons, the CRAB CTC Operations Office must be notified and the central IRB must be informed immediately. Amendments affecting only administrative aspects of the study do not require formal protocol amendments or IRB approval but the IRB must be kept informed of such administrative changes. Examples of administrative changes not requiring formal protocol amendments and IRB approval include:

- 1. changes in the staff used to monitor trials, and
- 2. minor changes in the packaging or labeling of study drug.

14.2 STUDY TERMINATION

Amgen and the CRAB CTC reserve the right to discontinue the study under the conditions specified in the clinical trial agreement.

14.3 STUDY DOCUMENTATION AND ARCHIVE

Records and documents pertaining to the conduct of this study, including CRFs, source documents, consent forms, laboratory test results, and medication inventory records must be maintained by the Investigator or Institution for the following length of time:

- For a period of at least 2 years after the last approval of a marketing application in an ICH region and until there are no pending or contemplated marketing applications in an ICH region; or
- At least 2 years have elapsed since the formal discontinuation of clinical development of the investigational product.

No study records shall be destroyed without prior authorization from Amgen and the CRAB CTC Operations Office.

14.4 DISCLOSURE AND CONFIDENTIALITY

The participating CTC investigator agrees to keep all information provided by Amgen and/or the CRAB CTC in strict confidence and to request similar confidentiality from his/her staff and the IRB/IEC/REB. Study documents provided by Amgen (such as Investigators' Brochures and other materials), and by the CRAB CTC (such as study protocol and other materials) will be stored appropriately to ensure their confidentiality. The information provided by Amgen and/or the CRAB CTC to the investigator may not be disclosed to others without direct written authorization from Amgen and the CRAB CTC Operations Office, except to the extent necessary to obtain informed consent from subjects who wish to participate in the trial.

14.5 PUBLICATION OF RESULTS

Any formal presentation or publication of data from this trial may be considered as a joint publication by the Sponsor-Investigator, participating CRAB CTC Investigators, Cancer Research And Biostatistics, and Amgen. For multicenter studies, it is mandatory that the first publication be based on data from all study sites, analyzed as stipulated in the protocol, and not by investigators acting solely on their own or their institution's behalf. Investigators participating on multicenter studies agree not to present data gathered from one study site or from a subset of study sites before the full, joint initial publication, unless formally agreed to by the Sponsor-Investigator, the CRAB CTC Operations Office, and Amgen.

Confidential

The CRAB CTC Operations Office and Amgen must receive copies of any intended communication in advance of publication (at least fifteen working days for presentational materials and abstracts and thirty working days for manuscripts). These requirements acknowledge CRAB's responsibility to provide peer input regarding the scientific content and conclusions of such publications or presentations. The Sponsor-Investigator and CRAB CTC Operations Office shall have the final authority to determine the scope and content of publications, provided such authority shall be exercised with reasonable regard for the interests of CRAB CTC and Amgen and, in accord with the trial contract and shall not permit disclosure of confidential or proprietary information.

14.6 STUDY MONITORING

14.6.1 PHASE IB ONLY: MANDATORY BI-MONTHLY TELECONFERENCES

A mandatory conference call will take place approximately twice a month during the registration period of the Phase Ib portion of the trial. Less frequent conference calls will be held after Phase Ib has completed. The call will update participating investigators on the current status of the trial and will include representatives from the study team (lead investigators, biostatisticians, and data management personnel), and investigators from all participating institutions. During the calls, adverse events encountered will be discussed and appropriate action taken. In between these regularly scheduled conference calls, participating investigators will be informed of important study decisions via email and by study announcements posted to the study website.

Institutional participation on the conference calls requires identification of an investigator contact and a CRC contact. Prior to registration of the first subject, each institution must provide contact names, email addresses, and phone numbers to the CRAB CTC Program Manager via email or Clinical Research Services main phone line: [contact]. Institutions will be responsible for keeping this information up-to-date and must notify the CTC Program Manager of any changes. The investigator and the contact CRC will receive e-mail reminders with the conference call information.

IST 14.6.2 PHASE II ONLY: MANDATORY QUARTERLY TELECONFERENCES

A mandatory conference call will take place approximately every three months during the registration period of the Phase II portion of the trial. The call will update participating investigators on the current status of the trial and will include representatives from the study team (lead investigators, biostatisticians, and data management personnel), and investigators from all participating institutions. During the calls, adverse events encountered will be discussed and appropriate action taken. In between these regularly scheduled conference calls, participating investigators will be informed of important study decisions via email and by study announcements posted to the study website.

Institutional participation on the conference calls requires identification of an investigator contact and a CRC contact. Prior to registration of the first subject, each institution must provide contact names, email addresses, and phone numbers to the CRAB CTC Program Manager via email or Clinical Research Services main phone line: [contact]. Institutions will be responsible for keeping this information up-to-date and must notify the CTC Program Manager of any changes. The investigator and the contact CRC will receive e-mail reminders with the conference call information.

14.6.3 SITE MONITORING

Monitoring procedures will be carried out by the Cancer Research And Biostatistics (CRAB) Study Monitor, and will be performed remotely on a regular basis to comply with Good Clinical Practice guidelines. Data and safety will be monitored by the sponsor-investigator, the biostatistician, and data management personnel. In addition, on-site monitoring visits will occur at least once during the study. Materials to be reviewed include the electronic case report forms (which will be cross-referenced with selected source documentation), study-related regulatory documents, and drug accountability logs.

At the conclusion of the on-site monitoring visits, the CRAB Study Monitor will complete a written monitoring report and forward it to the site Principal Investigator, the Sponsor-Investigator and to the CRAB Clinical Trial Consortium (CTC) Program Manager. The report will include a summary of what the Study Monitor reviewed and statements concerning the significant findings/facts, deviations and deficiencies, conclusions, actions taken or to be taken, and/or actions recommended to ensure compliance. The site Principal Investigator will be expected to submit any Corrective Action Plans, in writing, to the CRAB CTC Program Manager and the CRAB Study Monitor.

A copy of the monitoring materials, final monitoring reports, and Corrective Action Plan will be kept in the site monitor's study file at Cancer Research And Biostatistics for follow-up at the next monitoring session.

APPENDIX A: NCI-CTCAE VERSION 4.0

Common Terminology Criteria for Adverse Events (CTCAE) of the National Cancer Institute (NCI) v4.0

Publish Date: June 14, 2010 http://evs.nci.nih.gov/ftp1/CTCAE/CTCAE_4.03_2010-06-14_QuickReference_8.5x11.pdf

APPENDIX B: ASSESSMENT OF EFFICACY (RECIST 1.1 CRITERIA)

Criteria for Disease Response Evaluation Using RECIST 1.1 Criteria^[33]

1. Measurability of lesions.

a. Measurable disease.

- Lesions that can be accurately measured in at least one dimension (longest diameter to be recorded) as ≥ 2.0 cm by chest x-ray, as ≥ 1.0 cm by CT or MRI scans, or ≥ 1.0 cm with calipers by clinical exam. All tumor measurements must be recorded in decimal fractions of centimeters (or millimeters).
- 2) Malignant lymph nodes are to be considered pathologically enlarged and measurable if it measures ≥ 1.5 cm in **SHORT AXIS** when assessed by scan (CT scan slice recommended being no greater than 0.5 cm).
- b. Non-measurable disease. All other lesions (or sites of disease), including small lesions (longest diameter <1.0 cm or pathologic lymph nodes with ≥ 1.0 cm to <1.5 cm short axis), are considered non-measurable disease. Bone lesions, leptomeningeal disease, ascites, pleural/pericardial effusions, lymphangitis cutis/pulmonitis, inflammatory breast disease, and abdominal masses (not followed by CT or MRI), are considered as non-measurable as are previously radiated lesions that have not progressed.

c. Notes on measurability:

- 1.) For CT and MRIs, the same type of scanner should be used and the image acquisition protocol should be followed as closely as possible to prior scans. Body scans should by performed with breath-hold scanning techniques, if possible.
- 2.) The defined measurability of lesions on CT scan is based on the assumption that CT slice thickness is 0.5 cm or less. If CT scans have slice thickness greater than 0.5 cm, the minimum size for a measurable lesion should be twice the slice thickness.
- 3.) PET-CT: At present, the low dose or attenuation correction CT portion of a PET-CT is not always of optimal diagnostic CT quality for use with RECIST measurements. However, if the site can document that the CT performed as part of a PET-CT is of identical diagnostic quality to a diagnostic CT, then the CT portion of the PET-CT can be used for RECIST measurements and can be used interchangeably with conventional CT.
- 4.) Ultrasound: Ultrasound is not useful in assessment of lesion size and should not be used as a method of measurement.

- 5.) Cystic lesions that meet the criteria for radiographically defined simple cysts should not be considered as malignant lesions (neither measurable nor non-measurable) since they are, by definition simple cysts.
- 6.) If a target lesion becomes very small some radiologists indicate that it is too small to measure. If the lesion is actually still present, a default measurement of 0.5cm should be applied. If the radiologist believes the lesion has gone, a default measurement of 0.0cm should be recorded.

2. Objective status at each disease evaluation.

Objective Status is to be recorded at each evaluation. All measurable lesions up to a maximum of 2 lesions per organ and 5 lesions in total, representative of all involved organs, should be identified as target lesions at baseline. All other lesions (or sites of disease) including any measurable lesions over and above the 5 target lesions should be identified as non-target lesions. Measurements must be provided for target measurable lesions, while presence or absence must be noted for non-target measurable and non-measurable disease.

- a. Complete Response (CR): Complete disappearance of all target and non-target lesions (with the exception of lymph nodes mentioned below). No new lesions. No disease related symptoms. Any lymph nodes (whether target or non-target) must have reduction in short axis to < 1.0 cm. All disease must be assessed using the same technique as baseline.
- b. Partial Response (PR): Applies only to subjects with at least one measurable lesion. Greater than or equal to 30% decrease under baseline of the sum of appropriate diameters of all target measurable lesions. No unequivocal progression of nonmeasurable disease. No new lesions. All target measurable lesions must be assessed using the same techniques as baseline.
- c. Stable: Does not qualify for CR, PR, Progression or Symptomatic Deterioration. All target measurable lesions must be assessed using the same techniques as baseline.
- d. Progression: One or more of the following must occur: 20% increase in the sum of appropriate diameters of target measurable lesions over smallest sum observed (over baseline if no decrease during therapy) using the same techniques as baseline, as well as an absolute increase of at least 0.5 cm. Unequivocal progression of non-measurable disease in the opinion of the treating physician (an explanation must be provided). Appearance of any new lesion/site. Death due to disease without prior documentation of progression and without symptomatic deterioration (see 10.2e).

Notes regarding new lesions: FDG-PET imaging can complement regular scans in identifying new lesions according to the following algorithm.

1) Negative FDG-PET at baseline, with a positive FDG-PET at follow-up is a sign of progression based on a new lesion.

2) No FDG-PET at baseline and a positive FDG-PET at follow-up corresponding to a potential new site of disease must have a confirmation by anatomical assessment (e.g. CT, MRI, x-ray) as new site of disease to be considered progressive disease. In such a case, the date of progressive disease will be the date of the initial abnormal FDG-PET.

- e. Symptomatic deterioration: Global deterioration of health status requiring discontinuation of treatment without objective evidence of progression. Efforts should be made to obtain objective evidence of progression after discontinuation.
- f. Assessment inadequate, objective status unknown. Progression or symptomatic deterioration has not been documented, and one or more target measurable lesions have not been assessed or inconsistent assessment methods were used.
- g. Objective status notes:
 - 1. "Appropriate diameters" means short axis for lymph nodes; longest diameters for all other lesions,
 - 2. An objective status of PR or stable cannot follow one of CR. Stable can follow PR only in the rare case that tumor increases too little to qualify as progression, but enough that a previously documented 30% decrease no longer holds.
 - 3. In cases for which initial flare reaction is possible (hypercalcemia, increased bone pain, erythema of skin lesions), objective status is not progression unless either symptoms persist beyond 4 weeks or there is additional evidence of progression.
 - 4. Lesions that appear to increase in size due to presence of necrotic tissue will not be considered to have progressed.
 - 5. For bone disease documented on bone scan only, increased uptake does not constitute unequivocal progression. However, increase in the soft tissue component of a lesion as measured by CT or MRI would constitute progression.
 - 6. Appearance of new pleural effusions does not constitute unequivocal progression unless cytologically proven of neoplastic origin, since some effusions are a toxicity related to therapy or other medical conditions. Increase in the size of an existing effusion does not constitute unequivocal progression, since the fluid status of the subject could alter the size of the effusion.
 - 7. If CR determination depends on a lesion for which the status is unclear by the required tests, it is recommended the residual lesion be investigated with biopsy or fine needle aspirate.
- 3. Best Response. This is calculated from the sequence of objective statuses.
 - a. CR: Two or more objective statuses of CR a minimum of four weeks apart documented before progression or symptomatic deterioration.
 - b. PR: Two or more objective statuses of PR or better a minimum of four weeks apart documented before progression or symptomatic deterioration, but not qualifying as CR.

- c. Unconfirmed CR: One objective status of CR documented before progression or symptomatic deterioration but not qualifying as CR or PR.
- d. Unconfirmed PR: One objective status of PR documented before progression or symptomatic deterioration but not qualifying as CR, PR or unconfirmed CR.
- e. Stable/no response: At least one objective status of stable/no response documented at least 6 weeks after registration and before progression or symptomatic deterioration, but not qualifying as anything else above.
- f. Increasing disease: Objective status of progression at first assessment after registration, not qualifying as anything else above.
- g. Symptomatic deterioration: Objective status of symptomatic deterioration within 12 weeks of registration, not qualifying as anything else above.
- h. Inadequate assessment, response unknown: Progression or symptomatic deterioration greater than 12 weeks after registration and no other response category applies.

4. Performance Status

Subjects will be graded according to the Zubrod Performance Status Scale.

POINT DESCRIPTION

Fully active, able to carry on all pre-disease performance without
restriction.

- 1 Restricted in physically strenuous activity but ambulatory and able to carry out work of a light or sedentary nature, e.g., light housework, office work.
- 2 Ambulatory and capable of self-care but unable to carry out any work activities; up and about more than 50% of waking hours.
- 3 Capable of limited self-care, confined to bed or chair more than 50% of waking hours.
- 4 Completely disabled; cannot carry on any self-care; totally confined to bed or chair.

5. **Progression-Free Survival** From the date of registration to first documentation of progression or symptomatic deterioration (as defined in 2.d and 2.e), or death due to any cause. Subjects last known to be alive and progression-free are censored at date of last contact.

6. **Overall Survival** From the date of registration to the date of death due to any cause. Subjects last known to be alive are censored at date of last contact.

7. Time to Treatment Failure From date of registration to date of first observation of progressive disease (as defined in 2.d), death due to any cause, symptomatic deterioration (as defined in 2.e), or early discontinuation of treatment.

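### Appendix B leaves existing non-target measurable lesions out of the partial response and progression rules: read literally, their growth alone is not progression and does not block a PR

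*Combined protocol and SAP*

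**What the plan says.** All the relevant text is in Appendix B.

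- **Measurability (items 1.a and 1.b).** Measurable disease is "Lesions that can be accurately measured in at least one dimension (longest diameter to be recorded" at or above stated sizes, for example 1.0 cm on CT or MRI. Everything else, "including small lesions (longest diameter <1.0 cm or pathologic lymph nodes with ≥ 1.0 cm to <1.5 cm short axis), are considered non-measurable disease". The distinction rests on size and type of lesion, not on whether the lesion was chosen as a target.
- **Target cap (item 2).** Targets are chosen under this limit: "All measurable lesions up to a maximum of 2 lesions per organ and 5 lesions in total, representative of all involved organs, should be identified".
- **The remainder (item 2).** "All other lesions (or sites of disease) including any measurable lesions over and above the 5 target lesions should be identified as" non-target. Targets are measured, "while presence or absence must be noted for non-target measurable and non-measurable disease". The last phrase treats non-target measurable and non-measurable disease as two classes.
- **CR (2.a).** "Complete disappearance of all target and non-target lesions (with the exception of lymph nodes mentioned below").
- **PR (2.b).** "Greater than or equal to 30% decrease under baseline of the sum of appropriate diameters of all target measurable lesions", no new lesions, and no unequivocal progression of disease described as nonmeasurable.
- **Progression (2.d).** Any of: a 20% and 0.5 cm increase in the target sum; "Unequivocal progression of non-measurable disease in the opinion of the treating physician (an explanation must be provided"); a new lesion or site; death due to disease.

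The PFS definition in Appendix B item 5 refers to 2.d and 2.e. Section 8.1(b), on removal from treatment, refers to Appendix B section 2. Section 11.3 says only that RECIST criteria determine response and progression.

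**The concern.** The appendix defines a class of lesion, uses it for CR, and then omits it from PR and progression. A third liver metastasis of measurable size is outside the target sum because of the cap, is not non-measurable because of its size, and is not new. If it grows clearly while the targets are stable, no progression clause applies and the subject is scored stable. If the targets have shrunk by 30%, the subject is scored PR.

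Response rate and PFS are named Phase II secondary endpoints. A site that follows the text would date such a progression later than a site that takes the clause to mean all non-target disease. Section 3.2 expects at least 8 sites, and no central reading of scans for response or progression is described (the central review in Section 11.1 concerns eligibility). The difference would therefore pass into the data. The population is extensive-stage small cell lung cancer, in which more than 2 measurable lesions in an organ, or more than 5 in all, is plausible.

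**Working it through.** **Step 1. Trace each class of lesion through the rules.** The plan states no figure on this point to reproduce.

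| Class | CR (2.a) | PR (2.b) | Progression (2.d) |
|---|---|---|---|
| Target measurable | covered | covered | covered |
| Non-measurable | covered | covered | covered |
| New lesion | covered | covered | covered |
| Non-target measurable, already present | covered | not mentioned | not mentioned |

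**Step 2. An example with assumed sizes.** Five targets go from 10.0 to 6.5 cm: (6.5 - 10.0)/10.0 = -35%. A sixth measurable lesion goes from 3.0 to 6.0 cm (+100%). There is no new lesion and non-measurable disease is unchanged. As written, this is PR. With unchanged targets it would be stable.

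**Step 3. Look for a clause that closes the gap.** Note g.5, under which growth of a soft tissue component counts as progression, is confined to bone disease documented on bone scan only. Symptomatic deterioration (2.e) requires a global decline in health. Neither covers the case in general.

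**Step 4. Possible size for PFS.** The Phase II calendar puts scans on day 22 of cycles 2, 4 and 6, with 28-day cycles: 28 + 22 = day 50, 84 + 22 = day 106, 140 + 22 = day 162. The following are assumptions, not in the documents:

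- scans every 8 weeks after day 162;
- exponential time to progression, median 80, 110 or 140 days;
- death without progression, median 600 days, and an added risk of death after progression, median 100 days;
- progression dated at the next scan;
- a random 3-15% of progressions arising only in non-target measurable lesions, each dated one or two scans late.

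Simulated six-month PFS, 400,000 subjects per scenario:

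| Median time to progression | No delay | One scan late | Two scans late |
|---|---|---|---|
| 80 days | 0.196 | 0.199-0.209 | 0.202-0.224 |
| 110 days | 0.289 | 0.292-0.302 | 0.294-0.315 |
| 140 days | 0.360 | 0.362-0.372 | 0.364-0.383 |

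The shift is 0.2-1.3 points for one scan late and 0.4-2.8 points for two.

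Hand check at the top of the range (80 days, 15%, two scans late): a delay of two scans carries a subject past six months if true progression falls between days 50 and 162. That has probability 2^(-50/80) - 2^(-162/80) = 0.648 - 0.246 = 0.403, and 0.15 x 0.403 = 6.0 points before deaths. Deaths before six months bring this down to 2.8, so the result depends on the assumed death rates.

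For comparison, the standard error of a 25% rate at n = 40 is sqrt(0.25 x 0.75/40) = 0.068, or 6.8 points.

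**Step 5. Response rate.** Each subject scored PR who would otherwise not be moves a 40-subject stratum by 1/40 = 2.5 points. The documents give no basis for saying how often targets shrink by 30% while another measurable lesion clearly grows.

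**The case against.** The best reply is that this is a slip of wording. Section 11.3 invokes RECIST in general terms, the appendix is headed RECIST 1.1 and cites the published guideline, and note g.4 speaks of lesions generally when it exempts apparent growth due to necrosis. That suggests the drafter expected growth of any lesion to count. This is a fair account of intent. It does not close the gap, because PFS in Appendix B item 5 and removal in Section 8.1(b) point to the appendix's own definitions. If some readers rely on the general reference and others on the text, progression is dated by two rules.

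Other parts of the reply stand, and they rule out stronger readings that a reader might infer:

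- *That PR and progression look only at non-measurable disease.* They also act on the target sum and on new lesions. The gap concerns growth of an existing non-target measurable lesion, taken alone.
- *That recording presence or absence prevents progression from being declared.* The same record is kept for non-measurable disease, and 2.d still expects its progression to be judged, with an explanation.
- *That the text obliges sites to continue treatment.* Section 8.1(e) allows removal at the physician's discretion.
- *That PFS and response are known to be biased.* The share of such progressions and the delay are assumed. The simulation also assumes that every site reads the text literally; mixed reading would give a smaller shift. New lesions, symptomatic deterioration and death remain PFS events under the appendix, and a confirmed PR needs two qualifying assessments at least four weeks apart.

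**Conclusion.** The gap is in the current text: as written, the rule would score clear growth of a surplus measurable lesion as stable or PR. Any effect runs in one direction, towards later progression and more responses.

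Its size cannot be established from the documents. Under the assumptions above, six-month PFS shifts by about 0.2-2.8 points, less than half of the 6.8-point standard error even at the top. The effect on response rate is not estimated beyond 2.5 points per subject affected. Both are secondary endpoints with no test or decision threshold in Section 11.

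A reader might infer that the trial's main conclusion is at risk. The documents do not support that: the primary endpoint, the interim rule and the sample size rest on survival at six months, which does not use these definitions. This is a correction worth making because it is cheap and removes a difference between readers, not because the likely bias is large.

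**What to change.** In Appendix B 2.d, replace the reference to non-measurable disease in the unequivocal-progression clause with *non-target disease (measurable or non-measurable)*. Make the same replacement for nonmeasurable disease in 2.b. Both rules then use the class that item 2 defines and 2.a already applies.

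Optionally, let the response form record a non-target lesion as absent, present or unequivocally progressed. This helps documentation but is not essential to the correction.

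Section 8.1(b) borrows these definitions, so the sponsor should reconcile that reference at the same time. How it bears on stopping treatment is for the sponsor to settle.

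The cost is two changes of wording, with no extra scans, readers or subjects. The downside is that observed PFS and response rate may become slightly less favourable.
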